7.2 Qualitative data analysis

Qualitative data will be analysed using an inductive thematic approach (Guest et al., 2012) and managed through QSR NVivo 12 software. Thematic analysis is theoretically flexible, interpretive, and data driven, which will allow for uncovering the thoughts, perceptions, and feelings of the study participants (Grbich, 2012). The data analysis will focus on participant satisfaction (e.g. What did you like the most about the walking group?) as well as perceived outcomes of their involvement in the nature walking group (e.g. What do you think might be the impacts of the walking group for your mental health and wellbeing?). The team will collaboratively develop a codebook, and two researchers will code all the data sources independently and

compare their results. Additional strategies such as audit trail and member checking via the final data analysis workshop will be used to ensure rigor in our analysis (Meyrick, 2006).

7.3 Member-checking workshop

A group workshop will be conducted by investigators to invite Group A, B and C participants to engage with the data analysis process and clarify the findings thus far. Participants who attend will receive a \$50 payment for their time. During this workshop the investigators will engage with the participants in a process called member-checking whereby the participants are invited to provide feedback on the accuracy of the data analysis (McKim, 2023). Specifically, participants will be asked questions along the lines of ‘After hearing about the findings, what are your general thoughts?’; ‘How accurately do you feel the findings captured your thoughts/experiences?’; ‘What could be added to the findings to more accurately capture your experiences?’; ‘Is there anything you would like removed from the data, what would that be and why?’

8 DATA MANAGEMENT

Data Storage and Record Retention

The interviews will be audio-recorded and transcribed by professional transcribing services. We will keep the outcome measures, interview audios, interview transcripts and field notes in a Charles Sturt University password-protected one drive for business folder. The interview audio records will be destroyed after 5 years, which is the minimum storage period for University research. Only the researchers and trained and approved research assistants will have access to the data. Only the persons conducting the study or the person typing the information will hear the tape. All data collected from this study will be compiled so that no individual's statements are identifiable. The data will be owned by the Rural Health Research Institute of Charles Sturt University (see Attachment D for data management plan).

9 PROJECT TIMELINES

As shown in Table 5, the project is devised in three phases, 1) establishment, 2) implementation, and 3) analysis and finalisation. The implementation phase of the project will be conducted over eleven months, starting in April 2024 and data collection ceasing in January 2025.

In summary, the establishment phase of the project is as follows; 1) NWG facilitator training, 2) organisational wide readiness survey to be completed by trained NWG facilitators, 3) participant recruitment, project information sessions, screening and obtaining consent from walking and non-walking group participants. The implementation phase consists of 1) the data collection period where quantitative and qualitative is collected (e.g. salivary cortisol-DHEA measures, wellbeing outcome measures (pre- and post- intervention with 3 month follow-up), ethnographic observations, focus groups), and 2) the intervention period, where Group A individuals participate in the NWG. The analysis and finalisation phase comprises 1) the member-checking workshop, 2) data analysis, 3) finalisation of the evaluation and implementation guide, and 4) dissemination activities.

Given variations in weather patterns between the two study sites, the timing of the NWG will vary. Each site will run two separate NWG, each with 10 participants (four groups in total). While there is flexibility in the timing of each group, the timing of data collection will be the same for each group. The timing of the data collection is detailed in Table 6.

Table 5 - Project timelines

		Year/Month																	
		2024												2025					
		Jan	Feb	Mar	Apr	May	Jun	Jul	Aug	Sep	Oct	Nov	Dec	Jan	Feb	Mar	Apr	May	Jun
Establishment	Facilitator training, recruitment planning		x																
	Organisational readiness survey (C)				x														
	Participant recruitment (site information sessions)				x	x	x	x											
Implementation	Data collection period (A&B)				x	x	x	x	x	x	x	x	x						
	NWG intervention period (A)				x	x	x	x	x	x	x								
	Site-wide client data											x							
	Post intervention facilitator focus group (C)												x						
Analysis + finalisation	Member checking workshop (A&B)														x				
	Data analysis (incl. site comparisons)												x	x	x	x			
	Implementation and Evaluation Guide finalised															x			
	On-going dissemination																x	x	x

A = NWG group
 B = non-walking group
 C = NWG facilitators

Table 6 - Timing of data collection for participants (Group A and B)

	Week																										
Data collection	1	2	3	4	5	6	7	8	9	10	11	12	13	14	15	16	17	18	19	20	21	22	23	24	25	26	27
Pre/post salivary cortisol measure (A&B)**		x											x														
Pre/post & 3 month follow-up survey (A&B)	x												x													x	
NWG intervention (A)^		x	x	x	x	x	x	x	x	x	x	x	x														
Group closing reflective focus group (A)													x														
Post intervention phone interviews (A)															x												

A = NWG group

B = non-walking group

C = NWG facilitators

**Three measures of cortisol; one week prior to the first walk, at the conclusion of the first walk and at the conclusion of the final, twelfth walk

^Ethnographic observations, before and after mood scale

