5.4 Recruitment (Groups A and B)

The research team will attend a facilitator training to introduce the project and explain the research steps and processes. Recruitment flyers will be distributed at each of the study sites (See Appendix 12.1). Each location will have a study co-ordinator (TC, LikeMind, and PD, ICMHS) who hold managerial positions in each study site. The study site co-ordinator at each site will provide treating clinicians with an overview of the study and NWGs. Clinicians can then discuss participation with existing clients on their caseload and provide them with information on the study and the contact details of the research team. Some treating clinicians will also be trained NWG facilitators, however, they will not enrol potential participants into the study, or gain consent. Once all potential participants have been connected with the research team to express their interest, an information day will be conducted by research team members at each site. People who cannot attend the information session will be followed up by the research team.

Potential participants will receive a Participant Information Sheet (see Appendix 12.3) where they can learn more about the research project. Specifically, that participation in the NWG will involve:

- completing an online or pen and paper survey at the commencement and conclusion of the 12-week session,
- completing a brief mood question, pre- and post- each walk,
- participating in a walk once a week for 12 weeks at a location they will be transported to,
- participating in a 2 hour closing focus group at the 12th walk,
- completing one phone interview with a member of the research team, and
- providing 3 saliva samples for cortisol and DHEA testing one week before commencement, at the end of the first walk and conclusion of the last walk but that this will be **optional**.

If people consent to be part of the research, they will be invited to join the first walk. If they do not wish to join the NWG, or if they are not eligible to participate due to the results of the screening assessment (See Appendix 12.7), they will be allocated to Group B and provided a Participant Information Sheet (Appendix 12.4) which will include all details relating to the measures included in the survey to be completed at the beginning and end of a 12 week period, and the optional collection of a saliva sample for cortisol and DHEA testing at the same time as completing the survey.

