6.9 Phone interviews (Group A)

Individual phone interviews will be conducted with the participants of Group A 3 months after the intervention ends. A semi-structured interview guide will be used (see Appendix 12.11); interviews will be audiotaped and transcribed. The brief interview (15-30min) will explore any longer-term benefits for Group A including if they continued to walk in nature. The interviews will be conducted by the project investigators and/or research assistants.

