10 ETHICAL CONSIDERATIONS

10.1 Recruitment and Selection of Participants

Participants will be recruited through the existing caseloads of ICMHS and LikeMind, offering participation to any interested person, capping the number at ten for each NWG. Participants in the research will continue receiving the usual one-on-one support throughout the duration of the research. Participants will be recruited in March-April 2024, with the aim of beginning the NWG sessions at the end of April 2024 and concluding the first group in July 2024. The second group will commence in each site in approximately September, concluding in November. Start and finish dates may vary in each site depending on numbers of participants recruited and weather (too hot or cold). Consumers will be informed about the project by staff of the services. If they express an interest in participating, they will be provided with an information sheet and invited to a NWG information session facilitated by the research team. Consumers who are not interested in participating in the walking groups will also be invited to the study to be part of Group B. Consumers who are interested in participating in Group B will be invited to an information session facilitated by the research team where the study and data collection requirements will be explained, information sheets will be provided and consent to participate sought from volunteers. Potential participants who are unable to attend the information day will have a time organised to meet individually with one of the research team at the study site or via a phone call.

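### On the section 10.1 dates, the second walking groups' 3-month survey falls due after data collection closes, and Table 6 marks the 3-month phone interview at week 15

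*Protocol*

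**What the plan says.** Three places in the protocol fix the calendar.

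- **Section 9, text.** "The implementation phase of the project will be conducted over eleven months", "starting in April 2024 and data collection ceasing in January 2025". The same section says that each site runs two groups of ten, and that data-collection timing is the same for every group.
- **Section 9, Table 5.** Data collection is marked April to December 2024 and the walks April to October 2024. Data analysis is marked December 2024 to March 2025, and the member-checking workshop February 2025.
- **Section 10.1.** The first group runs from the end of April to July 2024. Then: "The second group will commence in each site in approximately September, concluding in November". Start and finish dates may vary by site with recruitment and weather.

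Table 6 gives the offsets. The row that begins "Pre/post & 3 month follow-up survey (A&B" is marked at weeks 1, 13 and 26, and the twelve walks occupy weeks 2 to 13. The row that begins "Post intervention phone interviews (A" is marked at week 15.

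Section 6.9 gives a different time for that interview: "Individual phone interviews will be conducted with the participants of Group A 3 months after the intervention ends". Its stated purpose is to look at longer-term benefit and whether people went on walking in nature.

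Section 5.4 tells prospective Group A members about "completing an online or pen and paper survey at the commencement and conclusion of the 12-week session" and gives Group B the same two time points. It does not mention the 3-month survey there. Sections 3, 6.6 and 10.3 all include that survey.

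**The concern.** The follow-up survey carries the primary outcome scale (PHQ-ADS) and is the only quantitative evidence on whether any effect lasts. If the second groups walk when section 10.1 says and collection stops when section 9 says, the site team must either skip their 3-month survey or take it early. Skipping it leaves the 3-month result resting on the first groups alone. Taking it early mixes different follow-up intervals under one label. Because the two sets of groups walk in different seasons, a loss confined to the second set would not be random.

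The phone interview raises the same kind of problem without depending on any calendar date. Staff cannot follow both section 6.9 and Table 6, and an interview two weeks after the last walk says much less about continued walking than one at three months.

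**Working it through.** **1. The plan's own figure.** The stated length of the implementation phase is eleven months. April 2024 to January 2025, counted inclusively, is 10 calendar months. Table 5 marks 9 for data collection (April to December). Neither reproduces eleven. Eleven months counted from April 2024 would run to the end of February 2025.

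**2. Offsets from Table 6.**
- Last walk = first walk + 11 weeks (weeks 2 to 13).
- Follow-up survey = last walk + (26 − 13) = last walk + 13 weeks.
- Phone interview = last walk + (15 − 13) = last walk + 2 weeks.

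**3. First groups.** A first walk on 29 April 2024 gives a last walk on 15 July and a survey on 14 October 2024. This is inside both windows.

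**4. Second groups, on the section 10.1 dates.**

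| Case | First walk | Last walk | Survey due | After 31 Jan 2025 |
|---|---|---|---|---|
| Earliest September start | 1 Sep 2024 | 17 Nov 2024 | 16 Feb 2025 | 16 days (2.3 weeks) |
| Latest November finish | 14 Sep 2024 | 30 Nov 2024 | 1 Mar 2025 | 29 days (4.1 weeks) |

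No September start brings the survey inside a window that closes on 31 January 2025, still less one that closes on 31 December 2024.

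**5. Working backwards from each close.**
- Close 31 January 2025: last walk by 1 November 2024, first walk by 16 August 2024.
- Close 31 December 2024: last walk by 1 October 2024, first walk by 16 July 2024.

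**6. Table 5 taken alone.** Last walks between 1 and 31 October 2024 put the survey between 31 December 2024 and 30 January 2025. Only a finish on 1 October meets Table 5's own December close.

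**7. Number affected.** Two of four groups of ten is 20 of 40 in Group A. The protocol does not say how many Group B members are followed on the second groups' timing.

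**8. Phone interview.** Table 6 gives 2 weeks after the last walk, against about 13 weeks in section 6.9. The gap is about 11 weeks.

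**9. Power at 3 months, for illustration only.** From section 7.1 the difference is 22.76 − 16.08 = 6.68, and the pooled SD is √[(9.46² + 10.41²)/2] = 9.95. By two-sample t-test at the 5% level:
- 36 v 36: power 0.80, which agrees with the plan.
- 18 v 36 (half of Group A lost, Group B complete): power 0.63.
- 18 v 18 (half of both groups lost): power 0.50.

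**The case against.** The strongest reply is that these are indicative dates. Section 10.1 calls September approximate and lets dates vary by site, section 5.5 allows groups to run simultaneously or consecutively, and section 9 allows flexibility in when each group runs. One combination does fit: Table 5's October end of walks with the January close in the section 9 text puts the last survey at 30 January 2025. That stands as a way to remove the conflict, but it contradicts the November finish in section 10.1. Ordinary flexibility around a September start does not reach the mid-August start that would be needed.

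A reader might infer that half of Group A has no 3-month survey. The protocol does not say that. Sections 3 and 6.6 require the survey for both groups, and section 10.3 pays for it. What is shown is that it falls due after the stated close.

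A reader might also infer that the study's power drops from 80% to 50%. That needs two things the protocol does not state: that Group B divides evenly between the two sets of groups, and that the power calculation concerns the 3-month time point. Section 7.1 bases its effect on a change immediately after the cited therapy and on distress after the programme, which points to the week-13 survey, although its mention of follow-up is ambiguous. The figures are also for a t-test, while the plan names the Wilcoxon signed ranks test.

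On the interview, section 6.9 is explicit and Table 6 is loose elsewhere: its saliva row has two marks while its footnote lists three samples. The week-15 mark may well be a slip, but it is still the schedule that staff would work from. It would be too strong to say that an interview at that point shows nothing about continued walking.

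Nor does section 5.4 show that participants go uninformed. Section 10.3 lists the follow-up survey among the consent contents, and the information sheets are not available to check.

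**Conclusion.** The timetable is wrong as written. On the section 10.1 dates, the week-26 survey for two of the four walking groups (about 20 of 40 in Group A), and for an unstated number in Group B, falls due some 2 to 4 weeks after a 31 January 2025 close, and later still relative to Table 5's December close. Table 5's own walk end and close do not fit together either. The Table 6 interview mark and section 6.9 differ by about 11 weeks.

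The effect is confined to the 3-month survey and the interviews; the week-13 PHQ-ADS comparison is untouched. Any loss of power applies only to the 3-month comparison, at about 63% or 50% depending on how Group B is split. The conclusion assumes that the September-to-November plan is followed and that Table 6 applies to every group, as section 9 says.

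**What to change.** 1. In section 9 and Table 5, extend data collection past the last week-26 survey: at least early March 2025 on the section 10.1 dates. Stating the close as no earlier than 13 weeks after the final walk of the last group would keep it correct if dates move. Correct the eleven-month figure to match.
2. Place the final data cut and the member-checking workshop after that survey.
3. Reconcile the end of the walks between Table 5 (October) and section 10.1 (November). If a January close is kept, the last walk must be by about 1 November 2024 and section 10.1 must say so.
4. In Table 6, move the phone-interview mark from week 15 to about week 26, to agree with section 6.9.
5. As a minor consistency edit, add the 3-month survey to both descriptions in section 5.4.

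No extra participants or visits are needed. Table 5 already runs analysis to March 2025, so the cost is a later workshop and data cut, with some knock-on delay likely for the guide (due March 2025) and dissemination (from April 2025).

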5.5 Intervention (Group A)

A total of four NWG over 12 months will be conducted in the two sites by the trained NWG facilitators. Intervention participants (n=40) will participate in one NWG, receiving 1 hour of time in nature for a continuous period of 12 weeks. Participants will be transported to and from each NWG location by the NWG facilitators. There will be no expectation to socialise with other group members but to remain in the group. Depending on weather variations in each location, the groups may be offered simultaneously or consecutively. Where available an educator such as a National Park ranger can join and refer to points of interest and answer any questions. The project funds will cover all costs of the intervention including backfill for clinicians if required.

5.5.1 *Relaxation and mindfulness activities*

Each NWG will take place in a natural environment, e.g., bush, countryside, National Parks, greenspace in urban areas (e.g., botanical gardens). Each walk will include two activities led by trained facilitator that draw participant's attention to one of the natural features of the site (water, birds, plants) and provide time to reflect on those features. The activities relate to psychological theories that link connection with nature as a pathway to health and wellbeing including Attention Restoration Theory (Ohly et al., 2016), and Stress Reduction Theory (Andrade & Devlin, 2015). Each activity is 2-10 minutes long and is matched with the optimal kind of nature known to facilitate a particular outcome. For example, nature with a high degree of textural diversity is known to be optimal for a stress reduction response. As shown in Table 2, several relaxation and mindfulness routines have been identified for possible inclusion in the NWG, and the study-site co-ordinators will finalise which routines and the locations where they will be used closer to the projects commencement. Each routine will include a script for facilitators to read, or there are audio versions that may be used (for example <https://www.naturefix.life/feel-the-flow>).

Table 2 – Summary of the relaxation and mindfulness activities under consideration for inclusion in the Nature Walking Group

Routine name	Summary	Length (minutes)
1. Tune in to tune out	This abdomen breathing routine takes participants through a simple breathing strategy to take more effective breaths to increase their relaxation and decrease any stress.	2-4

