7.1 Sample size and power calculation

While sample size calculation is crucial for a pilot study, achieving adequate power through formal calculations can be challenging (Billingham et al., 2013). Nonetheless, we have derived the sample size for this study by considering the estimated effect size observed in the literature for various mental health indicators. According to the conceptual framework of the proposed pilot feasibility trial study, the primary outcome measure was the level of distress measured by Patient Health Questionnaire Anxiety and Depression Scale (PHQ-ADS). In a recent randomized controlled trial study in the UK conducted by Picariello et al. (2024), it was found that the mean level of distress among the study participants was 22.76 (SD, 9.46), which decreased by 30% immediately after the cognitive behavioural therapy intervention. We utilized these study findings to inform the parameters for the sample size calculations in our study. We assumed the mean level of distress will be about 22.76 (with SD, 9.46) among the study participants at baseline in both control and interventions group (Picariello et al., 2024). After the program implementation, the mean level of distress will be reduced to 16.08 (SD, 10.41) among the participants in interventions group (assuming about 30% reduction by the intervention; Picariello et al. (2024). To ensure a minimum detectable difference in the mean distress level between the intervention and control groups at follow-up, with a power of 80% and a 5% level of significance, a minimum sample size of 72 participants is required (36 participants in each group). Anticipating 10% loss to follow-up, we plan to include 80 participants in total. Therefore, data will be collected from at least 40 participants in both the control and intervention groups, enabling to assess the program's effectiveness in improving mental health outcomes. Our planned sample size falls within the range of suggested sample sizes for pilot and feasibility studies as per the guidelines, which recommend 30-59 participants (Billingham et al., 2013; Viechtbauer et al., 2015).

The outcomes will be analysed using a Wilcoxon signed ranks test to calculate change between scores because measures contain ordinal data and a test that does not assume a normal distribution is required. A W-statistic is appropriate for a small number of linked observations.

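### The 80% power in section 7.1 holds only if Group A outcomes are independent, yet Group A is treated in four walking groups and no named test has a walking-group term

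*Protocol*

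**What the plan says.** **Structure.** Protocol section 9 sets out the delivery: "Each site will run two separate NWG, each with 10 participants (four groups in total". Section 5.5 places each person in a single group: "Intervention participants (n=40) will participate in one NWG, receiving 1 hour of time in nature for a continuous period of 12 weeks". Section 10.1 caps each group at ten and runs an earlier and a later group at each site. Section 5.5.2 describes joint transport, joint briefing and a shared reflection at every walk. Group B continues individual usual care (section 5.6) and has no comparable grouping.

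**Sample size.** Section 7.1 takes PHQ-ADS as primary outcome and concludes that "a minimum sample size of 72 participants is required (36 participants in each group", "with a power of 80% and a 5% level of significance". The only inflation is for attrition: "Anticipating 10% loss to follow-up, we plan to include 80 participants in total". It mentions no ICC, design effect or walking group.

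**Analysis.** Table 1 and section 7.1 name a Wilcoxon signed-rank test for the survey outcomes. The opening of section 7 names analysis of variance for efficacy. Both are described without a term for walking group.

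**The concern.** People who spend 12 weeks in the same small group share walks, weather, season and one another. Their outcomes are likely to be positively correlated. With grouping in one arm only, the design is partially nested, with just four clusters in that arm.

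If the correlation is positive, the effective size of Group A is below its headcount. Standard errors computed as if people were independent are then too small, p-values too low, and the power claim in section 7.1 too favourable. This matters because section 7.1 states a formal power and says the sample will let the team judge effectiveness, and section 7 presents the analysis as evidence of efficacy.

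**Working it through.** **Inputs from section 7.1.** Control: "We assumed the mean level of distress will be about 22.76 (with SD, 9.46) among the study participants at baseline in both control and interventions". The control mean and SD are taken as unchanged at follow-up, which the Protocol implies but does not state. Intervention: "the mean level of distress will be reduced to 16.08 (SD, 10.41) among the participants in interventions group". Difference = 22.76 − 16.08 = 6.68. Alpha is 5%; two-sided is assumed, and it reproduces the stated number.

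**Reproducing the plan's figure.** Pooled SD = √((9.46² + 10.41²)/2) = 9.95. A two-sample t calculation gives 79.1% power at 35 per group and 80.2% at 36. So 36 per group, or 72, is right under independence, and 72/0.9 = 80. The stated number therefore contains a design effect of exactly 1.

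**Adding the walking groups.** Assume 10% loss falls evenly, leaving four groups of m = 9 (36 in Group A) and 36 controls. The ICC is not in the Protocol; 0.02, 0.05 and 0.10 are assumed.

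- Design effect in Group A: DE = 1 + (m − 1) × ICC = 1 + 8 × ICC.
- Variance of the Group A mean: 10.41² × DE/36. Variance of the Group B mean: 9.46²/36 = 2.486.
- Naive standard error: SE₀ = √((10.41² + 9.46²)/36) = 2.344. True SE = √(sum of the two variances).
- Type I error of the naive test: 2 × [1 − Φ(1.96 × SE₀/SE)].
- Power on variance alone: noncentral t with noncentrality 6.68/SE and 70 df.
- Power with small-cluster df: the same noncentrality with Satterthwaite df = (V_A + V_B)²/(V_A²/c + V_B²/35). Here c = 3 for four clusters, or c = 2 if site is also fitted.

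| ICC | DE | V_A | SE | SE/SE₀ | Naive type I error | Power, variance alone | df and power, c = 3 | df and power, c = 2 |
|---|---|---|---|---|---|---|---|---|
| 0 | 1.00 | 3.010 | 2.344 | 1.00 | 5.0% | 80% | 9.4; 72% | – |
| 0.02 | 1.16 | 3.492 | 2.445 | 1.04 | 6.0% | 77% | 8.4; 68% | 5.7; 62% |
| 0.05 | 1.40 | 4.214 | 2.589 | 1.10 | 7.6% | 72% | 7.4; 61% | 5.0; 55% |
| 0.10 | 1.80 | 5.418 | 2.812 | 1.20 | 10.2% | 65% | 6.3; 52% | 4.2; 45% |

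**Separating the two sources of loss.** At ICC 0 the c = 3 correction alone takes power from 80.2% to 72.3%, a loss of 7.9 points with no clustering present. Moving from variance alone to c = 3 costs 9.4 points at ICC 0.02 (76.9% to 67.5%), 11.1 at 0.05 (72.1% to 61.0%) and 13.0 at 0.10 (64.9% to 52.0%). Most of that further step is the cost of estimating with four clusters.

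**What baseline adjustment could return.** Assume a pre-post correlation of 0.5 and the same ICC after adjustment. Both variances are multiplied by 1 − 0.5² = 0.75. Power on variance alone becomes about 84% at ICC 0.05 and 77% at 0.10; with c = 3 it is about 73% and 64%.

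**The case against.** **The size is assumed.** This stands. The Protocol gives no ICC, and at 0.02 the effect is 77% power against 80% and 6% type I error against 5%, which is modest for a study that calls itself a pilot. Some features also point to a low ICC: routines are to be matched across sites and groups (section 5.5.3), and participants are not expected to socialise (section 5.5). Only the direction, for any positive ICC, is firm.

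**The small-cluster powers look worse than the defect.** This stands. A reader might infer that ignoring the groups by itself cuts power to 68%, 61% and 52%. It does not, because power is already about 72% at ICC 0 under the same correction.

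**Power may not be overstated at all.** This stands in part. Section 7.1 takes no credit for the baseline score collected under section 6.6, and adjusting for it could offset some or all of the loss. But no such adjustment is stated, so the 80% as derived still rests on independence.

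**A statistical analysis plan may add a group term.** This does not remove the point. The Protocol itself fixes the sample size, the power figure and the signed-rank test. A later group term would not make the 80% correct, and a signed-rank test cannot carry a random effect.

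**It is only a pilot.** That lowers the stakes, but section 7.1 still states 80% power and an intention to judge effectiveness.

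**Conclusion.** The stated 80% power is conditional on an independence assumption that the Protocol's own delivery plan makes doubtful, and none of the named tests allows for the groups. Under assumed ICCs of 0.02 to 0.10, equal groups of 9 completers and an unadjusted comparison of follow-up means, naive type I error is about 6% to 10% and power on variance alone about 77% to 65%. With small-cluster degrees of freedom power is about 68% to 52%, or about 62% to 45% if site is also fitted.

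Two stronger readings are not supported. A reader might infer that reported confidence intervals will certainly be too narrow, but the Protocol specifies no intervals and gives no ICC. A reader might also infer that the study is too small and must grow, but that does not follow for a pilot whose ICC is unknown. These error rates are for the between-group comparison that the sample size assumes. The signed-rank test as named is a paired test and does not make that comparison.

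**What to change.** 1. In section 7.1, say that 36 per group gives 80% power only under independence, and show power for ICCs of about 0.02 to 0.10. Label the ICCs as assumptions and give the figures with and without small-cluster degrees of freedom. Do not enrol more people for this reason.
2. For the between-group comparison, replace the signed-rank test with a partially nested model of follow-up PHQ-ADS. Adjust for baseline PHQ-ADS, put a random effect for walking group in Group A only (each Group B participant standing alone), and use Satterthwaite or Kenward-Roger degrees of freedom. Bring Table 1 and the opening of section 7 into line.
3. Decide in advance whether site is fitted. With two walking groups per site it leaves about 2 cluster degrees of freedom.
4. Report any ICC from four groups as descriptive and very imprecise.

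**Cost.** No extra participants or visits. The named test changes, which is more than a wording edit: section 7.1 chose a rank test to avoid assuming normality, so residuals will need checking. Intervals will be wider and the stated power less favourable, though baseline adjustment may recover part of it. The model does not address the non-random choice between Groups A and B, which is a separate matter.
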